- i Resting TTE should be performed prior to post-exercise stress echocardiography or CPET. Resting TTE images and views will be acquired at each onsite visit prior to dosing as detailed in the echo site instruction manual. Instantaneous LVOT peak gradient (resting) and provoked LVOT peak gradient (Valsalva maneuver) will be assessed by the core laboratory. Left ventricular ejection fraction (LVEF) will be measured at the clinical site by the certified site sonographer and subsequently by the core laboratory. The LVEF site read will be kept blinded from the investigator and other study site personnel, except in case of locally measured LVEF $\leq$ 30%.
- j For post-exercise stress echocardiography, participants will undergo a standard symptom-limited exercise test after a 4-hour fast by standardized treadmill or bicycle ergometer during Screening and Week 30/EOT prior to dosing. Instantaneous LVOT peak gradient will be assessed immediately post-exercise by TTE. Post-exercise stress echocardiography may be performed on a different day than CPET. If the 2 procedures are performed on the same day, participants must exercise only once, and participants will undergo CPET and then post-exercise TTE. Post-exercise stress echocardiography should be acquired the same day or within 72 hours of the Resting TTE and should also be performed as close as possible to ET if it occurs. If post-exercise stress echocardiography and CPET are performed on different days, the same sequence of visits must be performed for both screening and EOT.
- k CPET by standardized treadmill or bicycle ergometer will be performed during Screening and at Week 30/EOT prior to dosing. CPET is done after a 4-hour fast. Record the fasting status and the date and time of the last dose taken prior to CPET. Any concomitant medication may be administered prior to all exercise testing. CPET should also be performed as close as possible to ET if it occurs.
- l A cardiac monitoring device will be applied during Screening, Week 12, and at the Week 26 visits and retrieved at the Day 1, Week 14, and Week 30 visits, respectively.
- m An accelerometer will be fastened to the participant's wrist at Screening (at least 11 days before Day 1) and at the Week 26 visit to collect data on activity. Participants will return the accelerometer at the next study visit for data upload and analysis.

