PRO Assessment a	Screening Day -35 to Day -1	Day 1	Week 4 (±7 d)	Week 6 (±7 d)	Week 10 (±7 d) (home)	Week 12 (±7 d)	Week 14 (±7 d)	Week 18 (±7 d)	Week 22 (±7 d)	Week 26 (±7 d)	Week 30/ EOT (±7 d)	Week 38/ EOS (±7 d)
█	X b	← →			X c		X c	X c				
█	X d			X	X		X	X	X	X	X	X
█				X	X		X	X	X	X	X	X
█		X		X		X		X			X	X
█		X		X		X		X			X	X
█		X		X		X		X			X	X

Abbreviations: d, day; EOS, end of study; EOT, end of treatment; EQ-5D-5L, EuroQol five dimensions 5-level questionnaire; home, PRO assessments completed at home; HCMSQ, Hypertrophic Cardiomyopathy Symptom Questionnaire; KCCQ-23, 23-item Kansas City Cardiomyopathy Questionnaire; PGIC, Patient Global Impression of Change questionnaire; PGIS, Patient Global Impression of Severity questionnaire; PRO, patient-reported outcomes; WPAI-SHP, Work Productivity and Activity Impairment questionnaire.

NOTE: Missed PRO assessments by patients outside of study visits are not considered protocol deviations.

a The PRO assessments that are completed at visits, with the exception of Screening, should be completed prior to any other study procedure taking place, where possible, and prior to any meaningful discussion about the study or study treatment with investigative site staff.

b Participants will receive a handheld electronic device and training at Screening. During Screening they will complete the HCMSQ daily for a minimum of 7 days and every day for the first 6 weeks after treatment initiation.

c Participants will complete the HCMSQ on the handheld electronic device daily for a consecutive 7-day (1-week) period prior to the Week 10, 14, 18, 22, 26, 30 (EOT), and 38 (EOS) time points.

d During Screening, participants will complete the PGIS on the handheld electronic device immediately following completion of the 1st and 7th day of the HCMSQ assessment. If the Screening periods is >7 days, the PGIS should also be completed immediately following completion of the 14th, 21st, 28th, and 35th day of the HCMSQ.

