### ***10.1.4 Management of Participants After Permanent Treatment Discontinuation***

If a participant permanently discontinues treatment prior to Week 30/EOT, the participant will be asked to undergo an ET visit as soon as possible after stopping study drug, using the procedure normally planned for the EOT visit, including post-exercise echocardiogram and CPET. Subsequently, every effort will be made to have the participant return to the site at the times corresponding to his or her remaining scheduled visits (ie, until the end of the study and including final CPET study at Week 30), or through the recovery or stabilization of any AE to be followed as specified in this protocol, whichever comes last.

Under circumstances of permanent treatment discontinuation, study participants can:

- Withdraw from treatment (permanent treatment discontinuation) and agree to participate in ET, EOT, and EOS visits. Participants are eligible to complete ET, EOT, and EOS visits only if they have received 22 weeks or more of study drug. If they have received less than 22 weeks of study drug, they are eligible to participate in the ET visit and visits up to EOT (week 30) but not beyond week 30.
- Withdraw from treatment (permanent treatment discontinuation) and agree to participate in the ET and EOT visit. This is the preferred follow-up for participants who have received less than 22 weeks of study drug.
- Withdraw from treatment (permanent treatment discontinuation) and agree to participate in the ET visit. This is the preferred follow-up for participants who have received study drug, regardless of treatment duration and who do not wish to be followed beyond ET visit.

- Withdraw from treatment (permanent treatment discontinuation) and all follow-up (see Section 10.2)

In case of difficulties to comply and return for all study visits until Week 30, every effort should be made to have the participant return for as many study visits as possible, especially the Week 30 visit with final CPET.

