Unless otherwise noted, nonsafety (ie. efficacy, pharmacodynamics [PD]) information displayed “by visit” will utilize analysis visits as defined by the analysis visit window as opposed to the visits at which the information was collected (ie, nominal visit). Data collected at unscheduled or early termination (ET) visits will also be mapped to analysis visits. The analysis day for the purposes of deriving the analysis visit windows are derived as follows (reference date is the study drug initiation date, or the randomization date if the study drug initiation date is missing):

- If date of information (year, month, and day) is completely missing, analysis day cannot be calculated and will be treated as missing. If the date is partially missing, date will be imputed according to the rules outlined in [Section 6.4](#).
- If date is < reference date, analysis day = date of information – reference date. If date \geq reference date, analysis day = (date of information – reference date) + 1.

The visit windows for efficacy and PD assessments will be defined according to their respective collection schedules. The rule for defining the analysis window is +/-14 days from the target visit date for all post-baseline visits, except for Week 30 and Week 38, which have +/- 28 day windows. If 2 adjacent visit windows overlap, the limits of the windows will be adjusted to the midpoint between the 2 visits. The specific window definitions for each endpoint are available in Appendix 2 [Table 3 to Table 9](#).

For efficacy and PD analyses, if a value does not fall within an analysis window, it will not be included in the summary analysis. However, these values will be included in data listings and SAS data sets. For post-baseline data, when more than 1 value is available within the same analysis visit, the value collected closest to the target visit day will be used for analysis. If 2 values are the same distance to the closest to target visit day (for example, 1 value is before and the other value is after the target day), then the latest value will be selected as the analysis value. For a specific analysis window, if the latest collected time point has 2 or more values collected, then for continuous data, the average among these results will be derived, and for categorical data (eg, yes or no) the clinically ‘worse’ value will be selected.

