14. SUMMARY OF CHANGES IN THE PROTOCOL PLANNED ANALYSES

APPENDIX 1.

Figure 1: Study Schema

Abbreviations: CPET, cardiopulmonary exercise testing; ECG, electrocardiogram; PK, pharmacokinetics; QD, once daily; stress echo, post-exercise stress echocardiography; TTE, transthoracic echocardiogram; wks, weeks.

Table 4: Schedule of Study Procedures

Table 4: Schedule of Study Procedures (Continued)

Assessment ^a	Screening ^b Day -35 to Day -1	Day 1	Week 4 (±7 d)	Week 6 (±7 d)	Week 8 (±7 d)	Week 12 (±7 d)	Week 14 (±7 d)	Week 18 (±7 d)	Week 22 (±7 d)	Week 26 (±7 d)	ET ^c	Week 30 (±7 d)/ EOT	Week 34 (±7 d) (call)	Week 38 (±7 d)/ EOS
FSH ^p	X													
Serum pregnancy test (women) ^q	X													
Urine pregnancy test (women) ^q		X	X		X	X		X	X	X	X	X	X	X
██████████		X												
██████████	X													
██████████		X									X	X		
Symptom Assessment														
NYHA functional classification	X	X	X	X	X	X	X	X	X	X	X	X		X
Patient-Reported Outcomes														
Investigational Medical Product														
IMP QD		←									→			
IMP administered at site ^t		X	X	X	X	X	X	X	X	X		X		
IMP compliance ^u			X	X	X	X	X	X	X	X	X	X	X	
Substudy														
██████████		X										X		

Abbreviations: AE, adverse event; BP, blood pressure; call, telephone contact; CMR, cardiac magnetic resonance imaging; CPET, cardiopulmonary exercise testing; CYP, cytochrome P450; d, day; DNA, deoxyribonucleic acid; ECG, electrocardiogram; EOS, end of study; EOT, end of treatment; ET, early termination; FSH, follicle-stimulating hormone; HCM, hypertrophic cardiomyopathy; HIV, human immunodeficiency virus; HR, heart rate; hs, high-sensitivity; ICD, implantable cardioverter-defibrillator; ICF, informed consent form; IMP, investigational medicinal product; LVOT, left ventricular outflow tract; NT-proBNP, N-terminal pro b-type natriuretic peptide; NYHA, New York Heart Association; PK, pharmacokinetic; PRO, patient-reported outcomes; QD, once daily; QTcF, Fridericia correction; SAE, serious adverse event; TTE, transthoracic echocardiography.

^a Preferred order of assessments is ECG, vital signs, PK, and TTE, all prior to study drug dosing unless otherwise described below.

^b Screening will require more than 1 visit to accommodate all of the study procedures.

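### Protocol Table 2 schedules no patient-reported outcomes at early termination, while Section 10.1.4 implies that they are collected; the two need to be reconciled

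*Protocol*

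**What the plan says.** **Questionnaires.** The column headers of Protocol Table 2 run from Screening through Week 26 to Week 30/EOT and Week 38/EOS. None is for ET. The HCMSQ is completed daily for the first six weeks, and then, under footnote c, over a "7-day (1-week) period prior to the Week 10, 14, 18, 22, 26, 30 (EOT), and 38 (EOS) time points". No footnote to Table 2 names an ET time point.

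**Other endpoints.** Protocol Table 1 and SAP Table 4 do have an ET column. Footnote k of Table 1 reads "CPET should also be performed as close as possible to ET if it occurs". Footnote j wants post-exercise echocardiography on the same day or "within 72 hours of the Resting TTE and should also be performed as close as possible to ET if it occurs". In SAP Table 4 the row "NYHA functional classification" is marked at ET.

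**Text on the ET visit.** Protocol Section 10.1.4 asks for it soon after study drug is stopped, "using the procedure normally planned for the EOT visit, including post-exercise echocardiogram and CPET". The same section allows follow-up to end there for participants treated "regardless of treatment duration and who do not wish to be followed beyond ET visit". Protocol Section 4 states that clinic visits in the double-blind period include PRO assessments. Section 9.6 refers to Tables 1 and 2 for the procedures at each visit.

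**Analysis.** SAP Section 6 states: "Data collected at unscheduled or early termination (ET) visits will also be mapped to analysis visits". It also states that "if a value does not fall within an analysis window, it will not be included in the summary analysis". SAP Section 6.5 ranks the KCCQ clinical summary score fourth and the HCMSQ shortness-of-breath score fifth among the secondary endpoints.

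**Not visible.** The row labels of Table 2, any PRO rows of Table 1 and SAP Table 4, Protocol Sections 9.1.3 and 9.1.4, and SAP Sections 8.1 and 8.2 cannot be read in the public documents. I take KCCQ-23 to be one of the three Table 2 rows marked at Day 1 and Weeks 6, 12, 18, 30 and 38, because SAP Table 10 gives that schedule for KCCQ-23, EQ-5D-5L and WPAI-SHP.

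**The concern.** A site, or whoever programs the handheld device, cannot tell whether questionnaires are due at an ET visit. Section 10.1.4 suggests yes; the PRO schedule suggests no. Exercise test, post-exercise echocardiogram and NYHA class are clearly due.

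The answer matters most for a participant who takes the ET-only option. If Table 2 is followed, nothing is recorded on either PRO endpoint at or after stopping, unless the ET visit happens to coincide with a scheduled PRO time point. KCCQ is not scheduled between Week 18 and Week 30, so for someone who stops just before Week 30 the last value may be 30 − 18 = 12 weeks old. For the HCMSQ the gap is shorter, because diaries are also scheduled before Weeks 22 and 26.

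Under SAP Section 6.4 missing values are in general not imputed and mixed models handle them implicitly. Whatever the model, it can only use what was collected.

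**Working it through.** **1. The SAP's own window.** Day 211 is the Week 30 target and the rule is ±28 days: 211 − 28 = 183 and 211 + 28 = 239. This reproduces SAP Table 6. For NYHA, Week 26 (day 183) is adjacent and the windows overlap, so the limit moves to the midpoint: (183 + 211)/2 = 197. This reproduces SAP Table 5.

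KCCQ has no Week 26 visit, and its Week 18 window in Table 10 ends at day 155. Nothing overlaps, so the rule gives a lower limit of 183. Table 10 prints 197.

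**2. Where an ET value lands** (SAP Tables 5, 6, 10 and 11). The last two columns apply only if the questionnaire is collected.

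| ET day | pVO2, LVOT gradient | NYHA | KCCQ | HCMSQ |
|---|---|---|---|---|
| up to 183 | not used | earlier visit, from day 16 | Weeks 6, 12, 18 on days 30-57, 72-99, 114-155; otherwise not used | earlier visit, from day 15 |
| 184-197 | Week 30 | Week 26 | not used | Week 26 (Week 30 on day 197) |
| 198-239 | Week 30 | Week 30 | Week 30 | Week 30 (to day 238) |

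If a Week 30 visit is also attended, the value nearest day 211 is used, and the questionnaires are scheduled at that visit.

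**3. Size of the Week 30 imbalance.** The documents give neither a rate of stopping without return nor the timing of ET visits. Assumptions: 2-8% of 220 stop and do not return, and ET days are spread evenly over days 1-211.

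- Non-returners: 220 × 0.02 = 4.4 to 220 × 0.08 = 17.6.
- Days 198-211 are 14 days: 14/211 = 6.6%.
- Week 30 pVO2, LVOT gradient and NYHA present, both PROs absent: 4.4 × 14/211 = 0.3 to 17.6 × 14/211 = 1.2 participants.
- Days 184-211 are 28 days: 28/211 = 13.3%. Week 30 pVO2 and LVOT gradient present, with or without NYHA: 4.4 × 28/211 = 0.6 to 17.6 × 28/211 = 2.3 participants.

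**4. What ET collection could add for KCCQ.** Usable days before the Week 30 window are 28 + 28 + 42 = 98. With days 198-211 that makes 98 + 14 = 112 of 211, or 53.1%. Starting the Week 30 window after day 183 adds 14 days: 126 of 211, or 59.7%. In participants this is at most 2.3-9.3 with Table 10 as printed and 2.6-10.5 after alignment. These are upper limits, because a scheduled value nearer the target day takes precedence in the same window. HCMSQ windows run without a gap from day 15 to day 294, but until Week 6 the daily diary already supplies a value close to stopping.

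**5. Does the text settle the matter?** The Section 4 sentence follows a count of ten scheduled visits, which Table 1 gives as Day 1 and Weeks 4, 6, 8, 12, 14, 18, 22, 26 and 30. ET is not among them. Nor does Table 2 follow that sentence throughout: Week 8 is a clinic visit and has no column in Table 2. Section 10.1.4 does cover ET, but an unplanned visit cannot supply a 7-day HCMSQ diary for the days before it unless the diary is already running.

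**The case against.** The strongest reply is that the plan already calls for questionnaires at ET. Section 10.1.4 imports the EOT procedures and Section 4 puts PROs at clinic visits. The redacted Sections 9.1.3 and 9.1.4, to which the protocol refers for the PROs, may say so outright. This stands as far as it goes: non-collection at ET is not established. It does not remove the conflict with Table 2, and none of the visible text provides an HCMSQ diary for an unplanned visit.

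A reader might infer that any ET visit yields Week 30 values for three secondary endpoints and none for the two PROs. The windows do not support that. Up to day 183 an ET visit gives no Week 30 value for any of the five, and on days 184-197 NYHA counts as Week 26. The protocol also presses for attendance at Week 30. Days 204-218 are the scheduled Week 30 visit window in any case, which leaves mainly days 198-203: 4.4 × 6/211 = 0.1 to 17.6 × 6/211 = 0.5 participants.

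A reader might also infer a biased PRO comparison across all 4 to 18 non-returners. The documents do not support that either. They do not say that participants who stop early do worse, and the model and missing-data rules for these endpoints are not visible. Protocol Section 12.4.6.2 mentions only ANOVA for continuous variables.

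Two practical objections also stand. With Table 10 as printed, a KCCQ taken on days 156-197 falls in no window and is dropped. A diary started once stopping is known partly measures symptoms off drug. The fix has to deal with both.

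**Conclusion.** The inconsistency is real: Table 2 has no ET time point, Section 10.1.4 implies one, and two ranked secondary endpoints depend on the answer. If Table 2 governs, participants who leave after the ET visit have no PRO scheduled at or after stopping.

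The effect on the Week 30 comparison is small, about 0.3 to 1.2 participants with the full imbalance. That figure rests on the two assumptions in the working, 2-8% stopping without return and evenly spread ET days; neither comes from the documents. Before day 198 the loss is mainly of a last value that could enter an earlier analysis visit. The conclusion also depends on what the redacted PRO sections say. If they contain an ET instruction, only Table 2 needs correcting.

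The point is worth acting on because the data cannot be recovered later and the change is cheap. The 96% power stated for the primary endpoint is unaffected.

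**What to change.** 1. Add an ET column to Protocol Table 2 that matches Section 10.1.4. KCCQ-23, PGIS, PGIC, EQ-5D-5L and WPAI-SHP are completed at the ET visit before other procedures. If the sponsor does not intend PROs at ET, Section 10.1.4 should say so.
2. Add an HCMSQ rule: the daily diary starts when discontinuation is notified, the ET visit is not delayed for it, and days completed after the last dose are identified in the data. Set this up as an ET event on the handheld device.
3. In SAP Table 10, change the lower limit of the KCCQ Week 30 window from 197 to 183, as the ±28-day rule in SAP Section 6 gives. A KCCQ from an ET visit on days 184-197 is then not discarded while a pVO2 from the same day counts.

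The cost is one table column, one device event, one changed window limit, and a few minutes of questionnaires at a visit that participants who stop are already asked to attend. No power figure or primary analysis changes.

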## LIST OF ABBREVIATIONS

ACCF	American College of Cardiology Foundation
AE	adverse event
AESI	adverse event of special interest
AHA	American Heart Association
ALP	alkaline phosphatase
ALT	alanine aminotransferase
ASA	alcohol septal ablation
AST	aspartate aminotransferase
BP	blood pressure
CEAC	Clinical Event Adjudication Committee
CFR	Code of Federal Regulations
cGMP	current Good Manufacturing Practices
CMH	Cochran-Mantel-Haenszel
CMR	cardiac magnetic resonance imaging
CPET	cardiopulmonary exercise test or testing
CRF	case report form
CV	cardiovascular
CYP	cytochrome P450
DILI	drug-induced liver injury
EC	ethics committee; refers to an IRB or IEC or equivalent
ECG	electrocardiogram
eCRF	electronic case report form
EDC	electronic data capture
ER	emergency room
EM	extensive metabolizers
EQ-5D-5L	EuroQol five dimensions 5-level questionnaire
EOS	end of study
EOT	end of treatment
ESC	European Society of Cardiology
ET	early termination
EV	expired ventilation
FDA	The United States Food and Drug Administration
FSH	follicle-stimulating hormone
GCP	Good Clinical Practice
HCM	hypertrophic cardiomyopathy
HCMSQ	hypertrophic cardiopathy symptom questionnaire
HF	heart failure
HIV	human immunodeficiency virus
HLGT	high-level group term
HLT	high-level term
HR	heart rate

IB	Investigator's Brochure
ICD	implantable cardioverter-defibrillator
ICF	informed consent form
ICH	International Council for Harmonisation of Technical Requirements for Pharmaceuticals for Human Use
IDMC	Independent Data Monitoring Committee
IEC	Independent Ethics Committee
IMP	investigational medicinal product
IRB	Institutional Review Board
ITT	intention-to-treat
IUD	intrauterine device
IUS	intrauterine system
IXRS	interactive response system
KCCQ-23	23-item Kansas City Cardiomyopathy Questionnaire
LV	left ventricular
LVEF	left ventricular ejection fraction
LVOT	left ventricular outflow tract
MAD	multiple ascending-dose
MedDRA	Medical Dictionary for Regulatory Activities
MR	mitral regurgitation
NASH	nonalcoholic steatohepatitis
NT-proBNP	N-terminal pro b-type natriuretic peptide
NYHA	New York Heart Association
oHCM	obstructive hypertrophic cardiomyopathy
OP	outpatient
PD	pharmacodynamics(s)
PGIC	Patient Global Impression of Change questionnaire
PGIS	Patient Global Impression of Severity
PK	pharmacokinetic(s)
PRO	patient-reported outcomes
PT	preferred term
pVO 2	peak oxygen consumption
QD	once daily
QTc	corrected QT interval
QTcF	QT interval with Fridericia correction
RER	respiratory exchange ratio
RNA	ribonucleic acid
SAD	single-ascending dose
SAE	serious adverse event
SAP	statistical analysis plan
SBP	systolic blood pressure
SC	Steering Committee
SCD	sudden cardiac death
SD	standard deviation

---

SOC	system organ class
SUSAR	suspected unexpected serious adverse reactions
T	time (variable)
$t_{1/2}$	terminal half-life
TBL	total bilirubin
TEAE	treatment-emergent adverse event
TTE	transthoracic echocardiography, transthoracic echocardiogram
ULN	upper limit of normal
US	United States
VAS	visual analog scale
VCO 2	carbon dioxide production
VE	expired ventilation
VF	ventricular fibrillation
VT	ventricular tachycardia
VO 2	oxygen uptake
WPAI-SHP	Work Productivity and Activity Impairment questionnaire

### **3 STUDY OBJECTIVES**

#### **3.1 Primary Objective**

The primary objective of this study is:

- To compare the effect of a 30-week course of mavacamten with placebo on clinical response comprising of exercise capacity and clinical symptoms in participants with symptomatic oHCM

